Inclusion/Exclusion	
Inclusion Criteria:
 
 Female 18 years of age or older Diagnosis of unilateral breast cancer-related lymphedema Stage I or early Stage II lymphedema without severe fibrosis at the time of enrollment ≥ 5% volume difference between affected and unaffected arm as verified via perometry (LymphaTech 3D scanner) Willing and able to give informed consent Willing and able to comply with the study protocol requirements and all study-related visit requirements 
Exclusion Criteria:
 
 In-home use of pneumatic compression device (PCD) within previous 3 months

	
 2. Therapist or self-administered manual lymph drainage (MLD) within previous 1 week 3. Mastectomy or lymph node removal on side without lymphedema 4. Bilateral lymphedema 5. Heart failure (acute pulmonary edema, decompensated acute heart failure) 6. Acute venous disease (acute thrombophlebitis, acute deep venous thrombosis, acute pulmonary embolism) 7. Active skin or limb infection/inflammatory disease (acute cellulitis, other uncontrolled skin or untreated inflammatory skin disease) on the arms or trunk 8. Active cancer (cancer that is currently under treatment, but not yet in remission) 9. Poorly controlled kidney disease (glomerular filtration rate < 30 mls per minute), hypoproteinemia, pulmonary hypertension, hypothyroidism, cyclic edema, or Munchausen Syndrome 10. Body Mass Index (BMI) >50 11. Any circumstance where increased lymphatic or venous return is undesirable 12. Currently pregnant or trying to become pregnant 13. Allergy to iodine
Treatment Duration	
A single treatment lasting:
 
 • FT-SW: Approximately 40 minutes OR • FT: Approximately 60 minutes
Number Planned	20 subjects randomized (minimum of 10 in each arm) with replacement of up to 5 early withdrawals.

TABLE OF CONTENTS

1.0	Contact Information	7
1.1	Sponsor Contact Information.....	7
1.2	Principal Investigator Information.....	7
1.3	Clinical Investigator Information	7
2.0	Abbreviations	8
3.0	Introduction.....	10
3.1	Background and Rationale.....	10
3.2	Device Description	10
4.0	Study Objective.....	13
5.0	Study Design.....	13
5.1	Endpoints	13
5.2	Subject Selection	14
5.3	Point of Enrollment and Randomization	15
5.4	Treatment Assignment and Duration.....	15
5.5	Study Timeline	15
6.0	Study Assessments.....	15
6.1	Screening/Baseline	16
6.2	Randomization.....	16

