4.0 Study Objective

The objective of the study is to demonstrate equivalency in treatment effect, as determined by objective measurements, between the novel simultaneous therapy cycle software and the FDA-cleared FT.

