5.1 Endpoints

To compare the effects of FT to FT-SW in BCRL patients after one treatment based upon:

- Lymphatic activation in the affected and contralateral limb using the investigational technique of near infrared-fluorescent (NIRF) imaging
- Swelling in the affected and contralateral limb as assessed using:
 - Perometry (LymphaTech 3D Scanner)
 - Local tissue water content (MoistureMeterD)
- Skin changes on the affected and contralateral limb as assessed by:
 - Skin thickness (Ultrasound)
- Safety

Table 1. Outcome Measures

Endpoint	Outcome Measure
Lymphatic activation	
 Proportion of subjects who show an increase in the number of functional vessels and/or area of dermal backflow per NIRF imaging of the affected and contralateral arm when comparing post-treatment values to pre-treatment values Proportion of subjects who show an increase of lymphatic propulsion events immediately after treatment
Changes in Swelling	
 Proportion of subjects who show a decrease in arm perometry (limb volume) when comparing post-treatment values to pre-treatment values for the affected and contralateral arm Proportion of subjects who show a decrease in local tissue water at target sites when comparing post-treatment values to pre-treatment values for the affected side Mean change in perometry and local tissue water post-treatment will be compared for all sites
Skin Changes	
 Proportion of subjects who show a decrease in skin thickness at target site when comparing post-treatment values to pre-treatment values for the affected side Mean change in skin thickness post-treatment will be compared for all sites
Safety	
 Adverse events will be presented in data listings

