8.12 NIRF Imaging

After all injections are made and the water content and skin thickness measurements are made, NIRF imaging will commence. From the images of each region, the lymphatic activation (anatomy and propulsion) will be quantified as follows:

- Intact, fluorescent lymphatic vessels observed before and after the treatment will be recorded as an increase in vessels, decrease in vessels, or no change. The two-dimensional, projected area or extent of dermal backflow, before and after treatment, will be quantified using ImageJ (NIH, Bethesda, MD) by adjusting the brightness of the images to 20% of the maximum pixel value and measuring the area of regions of interest drawn around fluorescent areas not associated with intact and well-defined (i.e., “normal”) lymphatic vessels.
- The rate of lymphatic propulsion events observed immediately before and after treatment will be quantified by counting the total number of propulsion events observed and dividing by the total observation time at each region of interest.

Prior to injection and after NIRF imaging is complete, digital photographs of the arms will be acquired. Images of the front and back of the arms will be acquired with the subject standing up and the arms held out away from the sides.

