16.0 Statistical Methods

For continuous variables, descriptive statistics will include the number of subjects (n), mean, standard deviation, median, inter-quartile range, minimum, and maximum, based upon subjects with reported data for the variable being analyzed.

Frequencies (numerator and denominator), percentages, and 95% confidence intervals will be displayed for categorical data. Percentages by categories will be based on the number of subjects with no missing (unreported) data for the specific variable being analyzed and the count of the patients for each individual level of the categorical variable (the level specific numerators). Percentages will add up to 100%, unless otherwise indicated.

There are no plans to impute missing data and there are no plans to explicitly report missing data (counts and/or percentages) in the tables for all variables as part of the planned study report content. Variations in the reported sample sizes within and/or between relevant tables can be used to ascertain insights into unreported data. In some cases, unreported data may be the result of it not being clinically relevant to a particular patient or may represent expected data that was not collected. Selected analyses pertaining to unreported and/or missing data may be discussed and considered as future findings warrant.

The feasibility nature of the study suggests that the statistical focus will be on estimation and hypothesis generation. Thus, formal statistical tests of hypotheses are not planned.

All data processing, summarization, and analyses will be performed using R Version 3.54.0 or higher.

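### Table 1 counts only subjects with an increase on NIRF imaging, so its named lymphatic measures pool vessel loss with no change, although section 8.12 records the two separately

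*Combined protocol and SAP*

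**What the plan says.** Section 8.12 sets out three NIRF readings. Intact vessels, compared before and after treatment, "will be recorded as an increase in vessels, decrease in vessels, or no change". Dermal backflow is measured as an area in ImageJ. Propulsion is a rate: events counted, divided by observation time.

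Table 1 in section 5.1 turns these into two outcome measures. The first is "Proportion of subjects who show an increase in the number of functional vessels and/or area of dermal backflow per NIRF imaging", for the affected and contralateral arm, comparing post-treatment with pre-treatment values. The second is "Proportion of subjects who show an increase of lymphatic propulsion events immediately after treatment". Both count increases only.

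The other efficacy endpoints in Table 1 also have proportions in one direction, but each is paired with a mean change: "Mean change in perometry and local tissue water post-treatment will be compared for all sites" and "Mean change in skin thickness post-treatment will be compared for all sites". Lymphatic activation has no such line.

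The purpose is stated in section 4.0: "The objective of the study is to demonstrate equivalency in treatment effect, as determined by objective measurements". The synopsis plans "20 subjects randomized (minimum of 10 in each arm) with replacement of up to 5 early withdrawals". Section 16.0 plans estimation without formal tests. It says "Frequencies (numerator and denominator), percentages, and 95% confidence intervals will be displayed for categorical data", with counts for each level of a categorical variable, and it lists the usual summaries for continuous variables. It names no NIRF variable.

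**The concern.** The vessel reading has three levels and the Table 1 measure has two. A subject whose vessels decrease and a subject whose vessels do not change both fall into the not-increased group. The propulsion measure likewise puts a subject whose rate falls with one whose rate stays the same.

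A shorter treatment can differ from the standard one in two ways: fewer subjects may improve, or more may get worse. The named lymphatic measures can show only the first. For swelling and skin thickness, the mean change gives the second a chance to appear. For vessels, section 8.12 asks for a direction of change and not a count, so the decrease level is the only place where worsening can be read.

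This matters because the stated aim is equivalency, which calls for measures able to tell the devices apart. With no formal test planned, the choice of what to tabulate carries the weight. Section 17.0 also says that the data are meant to support product development and marketing claims.

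**Working it through.** The plan gives no margin, power or effect size that bears on this point, so there is no figure to reproduce. The check is of the outcome definition, with illustrative counts at the planned size.

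**Inputs.** 10 per arm (synopsis); three vessel levels (section 8.12); composite with backflow area (Table 1); 95% intervals (section 16.0). Assumed: the counts, and the exact Clopper-Pearson method, because section 16.0 names none.

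**Step 1. How the readings map to the measure.** A subject scores 1 if vessels increase or backflow area increases, otherwise 0.

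| Vessel reading | Backflow area increased | Backflow area not increased |
|---|---|---|
| Increase | 1 | 1 |
| No change | 1 | 0 |
| Decrease | 1 | 0 |

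The last two rows are identical. Whatever backflow does, the measure cannot separate vessel loss from no change. A subject who loses vessels scores 1 if backflow area rises.

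**Step 2. Illustration.** Assume that no subject without a vessel increase has increased backflow area. The score is then the number with a vessel increase divided by 10.

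| | FT | FT-SW |
|---|---|---|
| Increase / no change / decrease | 6 / 4 / 0 | 6 / 0 / 4 |
| Table 1 score | 6/10 = 60% (26.2 to 87.8%) | 6/10 = 60% (26.2 to 87.8%) |
| Proportion decreased | 0/10 = 0% (0 to 30.8%) | 4/10 = 40% (12.2 to 73.8%) |
| Increase minus decrease | 6 − 0 = +6 | 6 − 4 = +2 |

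For 0/10 the exact upper limit is 1 − 0.025^(1/10) = 0.308. The Table 1 difference is 60 − 60 = 0 points, and the difference in the proportion decreased is 40 − 0 = 40 points.

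**Step 3. The extreme case, same assumption.** If all 10 subjects in one arm are unchanged and all 10 in the other lose vessels, both arms score 0/10 (0 to 30.8%). The proportion decreased is 0% (0 to 30.8%) against 100% (69.2 to 100%).

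**Step 4. Relaxing the assumption.** Return to Step 2 and let backflow area increase in k of the 4 subjects per arm without a vessel increase, k from 0 to 4. That arm scores (6 + k)/10, from 60% to 100%. The FT-SW minus FT difference can then lie anywhere from 60 − 100 = −40 to 100 − 60 = +40 points, while vessel loss stays at 0% against 40%. The exact tie depends on the assumption; the pooling does not.

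**Step 5. Does pooling always make the arms look alike?** No. Take FT 6/0/4 and FT-SW 2/8/0 (increase/no change/decrease), again with no increased backflow area among those without a vessel increase. Table 1 shows 60% against 20%, a gap of 40 points, yet increase minus decrease is 6 − 4 = +2 and 2 − 0 = +2. Here the two-level measure shows a larger gap than the net change does.

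**The case against.** The strongest reply is that section 16.0 already covers this. If the vessel variable is tabulated as recorded, its level-specific counts show the decreases. If propulsion rate and backflow area are summarised as continuous variables before and after treatment, a fall in one arm would be seen. This stands in part: a reader might infer that worsening is dropped from the study and visible nowhere, and the documents do not support that. But the rule is general. It names no NIRF variable, promises no change scores and commits to no between-arm comparison of decreases, while the measure that Table 1 does name has no worse level.

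Second, a reader might infer that pooling pushes the comparison towards equivalence. Step 5 shows that the direction depends on the data. The plan also sets no margin and no test, so no equivalence decision follows automatically from this proportion.

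Third, the example is constructed, and nothing in the documents suggests that pattern. Even 0/10 against 4/10 has overlapping exact intervals and a two-sided Fisher p of about 0.09 (2 × 210/4845 = 0.087). That is fair. The counts show what the measure can hide and predict nothing, and small numbers are no reason to leave a recorded level out of an estimation study.

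Fourth, propulsion is a continuous rate. Apart from exact ties, nearly every subject would be classed as up or down, and the plan defines no tolerance for no change. A three-level split would label measurement noise as worsening. This stands and shapes the fix.

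**Conclusion.** The point holds as a gap between what is recorded and what the outcome measure uses. The Table 1 lymphatic measures cannot separate worsening from no change, and lymphatic activation is the only efficacy endpoint there without a mean change to make up for it. A real difference in vessel loss, 40 points in the illustration, can sit behind identical Table 1 results. That tie rests on the assumed counts and on no increase in backflow area among subjects without a vessel increase.

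The point reaches no further. It concerns the lymphatic measures; the swelling and skin outcomes could still differ between arms. It does not show that worsening would go unseen, only that the plan does not commit to showing it. It does not show a bias in a fixed direction. It does not invalidate the study, but it should be corrected, because the aim is equivalency and the information is already collected.

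**What to change.** In Table 1, lymphatic activation:

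- Report the vessel reading by arm and limb at its three recorded levels, separately from dermal backflow. Give the FT-SW minus FT difference with a 95% CI for the proportion increased and for the proportion decreased.
- For propulsion rate and backflow area, add the mean (or median) change from before to after treatment by arm and limb, with the between-arm difference and 95% CI. This matches what Table 1 already plans for swelling and skin thickness and needs no tolerance for no change.
- Name the interval method in section 16.0.

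The cost is a few more descriptive contrasts, with wide intervals at 10 per arm, to be read as estimates. No new data, visits or procedures are needed.

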8.13 Randomization

If the subject meets all of the inclusion criteria and none of the exclusion criteria, they will be randomly assigned to FT or FT-SW. The appropriate unblinded staff

member will obtain the randomization assignment by entering the appropriate randomization CRF in the EDC system.

The randomization assignment cannot be changed or chosen by the subject or the investigator.

8.14 Treatment

After all pre-treatment assessments have been performed, the subject will undergo the treatment that they have been randomized to. The personnel administering the treatment will not perform any study assessments as they will be unblinded to the treatment. If the subject has been randomized to the FT-SW, treatment will begin approximately 20 minutes after they enter the room where treatment is being performed to ensure the blinded study staff remain unaware of the treatment allocation.

8.15 Adverse Event Assessment

Adverse event assessment will occur during the acute study period and ~24 hours after the acute study.

Reportable events, as defined below, will be recorded on the subject's case report forms (CRFs).

8.15.1 Adverse Event (AE)

An adverse event is any untoward medical occurrence in a clinical research study subject which may or may not be related to use of the medical device under investigation.

Adverse events will be reported to the IRB in accordance with IRB policy.

8.15.2 Serious Adverse Event (SAE)

A serious adverse event is an untoward medical occurrence where the outcome is:

- Death;
- Life-threatening event (places the subject at immediate risk of death from the experience as it occurred);
- Hospitalization (initial or prolonged) if admission to hospital was warranted as a result of an adverse event;
- Disability or permanent damage (substantial disruption of one's ability to carry out normal life functions);
- Congenital anomaly or birth defect;
- Required intervention to prevent permanent impairment or damage; or
- Important medical event that required medical or interventional treatment to prevent one of the previous outcomes.

Investigators must report all Serious Adverse Events (SAEs) to Tactile Medical within 10 work days of becoming aware of the event. SAEs will

be summarized in writing and reported to the IRB in accordance with IRB policy.

8.15.3 Unanticipated Adverse Device Effect (UADE)

A serious adverse effect on the health or safety or any life-threatening problem or death caused by, or associated with, a device, if that effect, problem, or death was not previously identified in nature, severity, or degree of incidence in the product labeling, published literature, or Investigational Plan, or any other unanticipated serious problem associated with a device that relates to the rights, safety, or welfare of subjects.

Investigators must report all Unanticipated Adverse Device Effects (UADEs) to Tactile Medical within 10 work days of becoming aware of the event. UADEs will be summarized in writing and reported to the IRB in accordance with IRB policy.

8.15.4 Device Observations

Device observations will be recorded and reported to Tactile Medical. Device observations include device failures, device malfunctions, use errors, device issues, and user preferences, as defined below:

- **Device Failure:** A device failure has occurred when the device is used in accordance with the IFU, but does not perform as described in the IFU and also negatively impacts treatment of the study subject.
- **Device Malfunction:** A device malfunction occurs when an unexpected change to the device that is contradictory to the IFU is observed, which may or may not affect device performance.
- **Use Error:** A device use error is an act or omission of an act that results in a different medical device response than intended by the manufacturer or expected by the user. Use error includes slips, lapses, and mistakes. An unexpected physiological response of the subject does not itself constitute a use error.
- **Device Issue:** Any other issue with the device that does not fall into one of the above categories.
- **User Preference:** Information on user expectations, likes, dislikes, motivations, and inclinations that drive subject satisfaction with the device.

9.0 Subject Discontinuation or Withdrawal

Subject participation may be discontinued prior to study completion for any of the following reasons:

- **Withdrawal of Consent**

Subjects may withdraw their consent to participate at any time. If a subject withdraws consent, previous information that has already been obtained will be available for analysis.

- **Adverse Event**

Subject experiences an adverse event that in the investigator's clinical judgement necessitates discontinuation of their participation in this study.

- **Discretion of the Principal Investigator**

Subjects may be withdrawn at the investigator's discretion in the event of subject noncompliance, changes in the subject's health, or other reasons based on the investigator's clinical judgment.

When a subject withdraws prior to completing the study, the reason for withdrawal will be documented in the subject's record, and up to five replacement subjects may be enrolled to complete the cohort.

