5.3 Point of Enrollment and Randomization

Subjects will be considered enrolled in the study once the Informed Consent Form is signed and all inclusion/exclusion criteria are met. The investigator will keep a record, the subject screening log, of subjects who enter screening. Any subjects who do not meet inclusion/exclusion criteria will be considered screen failures.

Randomization codes will be generated by a Statistician in a permuted block design. The block size will be balanced within each block and will maintain a 1:1 ratio between the treatment groups. The randomization assignment will be obtained from the database and assigned sequentially as soon as an eligible subject completes the pre-treatment measurements.

If a subject does not meet all the eligibility criteria or meets any of the exclusion criteria but is randomized in error, or incorrectly started on treatment, the Investigator should inform Tactile Medical immediately.

Up to 5 enrolled subjects may be replaced if the subject is withdrawn prior to completion of the study. If a subject withdraws from participation in the study, his or her randomization code cannot be reused.

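### Replacement of withdrawn subjects, a non-missing denominator and no count of withdrawals by arm together give a completers-only comparison that can obscure arm-related treatment failure

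*Combined protocol and SAP*

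**What the plan says.** - **Number planned (Synopsis):** "20 subjects randomized (minimum of 10 in each arm) with replacement of up to 5 early withdrawals".
- **Who may be replaced (Section 5.3):** "Up to 5 enrolled subjects may be replaced if the subject is withdrawn prior to completion of the study". Neither this section nor Section 9.0 limits replacement by arm or by reason. Section 9.0 lists withdrawal of consent, adverse events and investigator discretion as reasons for leaving, then adds that "up to five replacement subjects may be enrolled to complete the cohort".
- **How a replacement is allocated (Section 5.3):** codes come from permuted blocks of unstated size at 1:1. They are "assigned sequentially as soon as an eligible subject completes the pre-treatment measurements". For a subject who withdraws, "his or her randomization code cannot be reused". A replacement therefore takes the next code, whichever arm it carries.
- **Denominator (Section 16.0):** "Percentages by categories will be based on the number of subjects with no missing (unreported) data" for the variable in question. Continuous summaries likewise use subjects with reported data. Nothing is imputed.
- **Reporting of missingness (Section 16.0):** "there are no plans to explicitly report missing data (counts and/or percentages) in the tables" for all variables. Readers are to draw what they can from differences in sample size between tables, and further analyses of missing data are left open.
- **What is kept (Section 9.0):** data collected before consent is withdrawn remain usable, and the reason for withdrawal goes into the subject's record.

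The document defines no all-randomised population and plans no table of withdrawals by arm.

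**The concern.** The swelling, skin and lymphatic outcomes in Table 1 are nearly all pre-to-post comparisons. A subject who stops during the session and is not tested afterwards cannot contribute to them, and her baseline data cannot supply the missing half. Her place can then be refilled, so the number with post-treatment data returns to about the planned size and the loss is hard to see from sample size alone.

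This matters because of the aim. Section 4.0 sets out to show equivalent treatment effect, and Section 17.0 intends the data for product development and marketing claims. FT-SW differs from FT by running two waves at once (Section 3.2.2). If that made some subjects stop, they would be the treatment failures of most interest, and they would be missing from the proportions being compared. The completers who remain would make the arms look more alike than the randomised groups were.

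**Working it through.** **The plan's own figure.** The document gives no power, margin, response rate or withdrawal rate, so there is no sample size calculation to reproduce. The available figures are 20 randomised, at least 10 per arm and up to 5 replacements, hence at most 20 + 5 = 25 codes. The cap is 5/20 = 25% of the planned number.

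**How many subjects an arm can hold.** Block size is not stated, so a range is needed.
- Blocks of 2 or 4: the first 24 codes split 12/12 and the 25th adds one, so an arm holds at most 13.
- Blocks of 10: the first 20 codes split 10/10. An arm reaches 15 only if codes 21 to 25 all fall in it, with probability 1/C(10,5) = 1/252 = 0.4% for a given arm.

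**Effect of the denominator.** Let c be the completers in an arm, w the randomised subjects who stop without a post-treatment value, and x the completers who improve. The plan reports x/c. Counting those who stopped as not improved gives x/(c + w). The second figure is the first multiplied by c/(c + w).

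*Illustration (assumed counts).* Two withdrawals, both from FT-SW, bring the codes used to 22. With blocks of 2 these split 11/11, leaving 11 − 2 = 9 completers in FT-SW. Suppose 7 of them improve.
- As planned: 7/9 = 77.8% (exact 95% CI 40% to 97%).
- On all randomised: 7/11 = 63.6% (31% to 89%).
- Shift: 77.8 − 63.6 = 14.1 percentage points before rounding (14/99).

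If nobody stops in FT, its proportion is the same on either denominator, so the whole 14 points passes into the difference between arms, in favour of FT-SW.

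*Outer bound.* All five withdrawals in one arm, that arm holding 13, and all 13 − 5 = 8 completers improved: 8/8 = 100% (63% to 100%) as planned, against 8/13 = 62% (32% to 86%). Five is the cap on replacements, not an expected number.

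**Completers per arm.** Start from 10/10 and lose one randomised subject. The arm that lost her returns to 10 only if code 21 falls in that arm, which has probability 1/2. For five withdrawals falling at random among the first 20, simulation gives a probability of 0.28 to 0.35 that both arms have 10 completers, for blocks of 2, 4, 6, 10 or 20. This costs little precision: for 8 against 12, √[(1/8 + 1/12)/(2/10)] = 1.02, a standard error about 2% larger. Bias is the issue, not imbalance.

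**The case against.** The case against is substantial, and much of it stands.

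- **Few subjects may be affected.** Treatment is a single session of about 40 or 60 minutes, and testing starts within about 15 minutes of its end (Section 6.4). Enrolment comes before randomisation (Sections 5.3 and 6.2), so some withdrawals will occur before any arm exists. Others may occur after same-day testing but before the 18 to 28 hour contact, with every pre-to-post value in hand. Neither kind biases these outcomes. The document also does not say that stopping treatment early means missing the post-treatment tests. The point concerns only those who are randomised and then not tested.
- **A reader might infer that a withdrawn subject disappears from the whole analysis.** The document does not support that. Denominators are specific to each variable, and data already collected are kept. She remains in the baseline summaries, the adverse event listings and any outcome already measured.
- **A reader might infer that replacement on the next code breaks the ten-per-arm minimum.** The synopsis attaches that minimum to subjects randomised, and replacements can only add to that count. It is not a promise of 10 completers, although the wording leaves room for that reading.
- **A reader might suppose that an arm could combine 10 completers with 5 withdrawn subjects.** That needs 15 in one arm, which blocks of 2 or 4 cannot produce and blocks of 10 almost never do.
- **A reader might infer concealment.** Reasons are recorded, numerators and denominators are shown, and Section 16.0 points readers to varying sample sizes. That safeguard is weak here, because replacement refills the count and because a lower n has other causes, such as ultrasound borders too unclear to measure (Section 8.11). The loss is obscured, not suppressed.
- **The study is for estimation, without formal tests.** True, but when the product is an estimate, its denominator is central to what it means.

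**Conclusion.** The concern holds in a limited form. Sections 5.3, 9.0 and 16.0 together set a rule: replace on the next code whatever the arm or reason, compute on non-missing values, and plan no count of the losses. For randomised subjects without post-treatment values this is a completers-only comparison. It is biased toward equivalence if stopping is related to the FT-SW software.

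The size depends on a withdrawal rate that the document does not give. With no such withdrawals the effect is nil; with two of 11 it is about 14 percentage points in the illustration, well inside the wide intervals that arms of this size give. Both figures assume that everyone who stopped counts as not improved. Nothing in the document shows that FT-SW is less well tolerated. The weakness is that the planned tables would not clearly show it if it were. This is a worthwhile and inexpensive improvement, not a fatal flaw.

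**What to change.** In Section 16.0:

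1. Add a disposition table by arm giving subjects randomised, treated, completed and withdrawn, with reasons.
2. Beside each completer proportion, report the proportion on all randomised and treated subjects. Count as not improved those who stop treatment for an adverse event or intolerance and have no post-treatment value. Say how subjects missing for other reasons are handled.

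In the synopsis, state that the ten-per-arm minimum means subjects randomised, and that about 10 per arm with post-treatment data are expected.

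The cost is one table, one extra column per proportion and one reworded line. Some proportions may look less favourable.

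Reserving replacement codes for the arm that lost a subject is not recommended. Unblinded staff obtain the assignments (Section 8.13), so anyone who knew the withdrawn subject's arm could predict the next allocation, and the gain in precision is only about 2% even at 8 against 12.
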